### **3.16 Clinical Laboratory Assessments**

The following laboratory tests will be done at screening and end of study. Subjects should be fasting, which means no food or drink (other than water) for at least eight hours prior to

sampling. Safety labs with a Grade 1 value will not exclude a subject from participation but will serve as their baseline value.

**Table 3-3: Laboratory Evaluations**

Category	Evaluation items
Hematology	Hemoglobin, WBC with differential, absolute neutrophil count and platelet count. MCV, MCH, MCHC, RDW, MPV.
Chemistry	Serum creatinine, BUN, calcium, total bilirubin, direct bilirubin, indirect bilirubin, alkaline phosphatase, PT, PTT, INR, ALT, AST, sodium, potassium, and total CK.
Urinalysis	Dipstick: Urine protein, blood and glucose. Menstruating females failing with a positive blood on urine dipstick may be retested following cessation of menses.
Other tests	Viral Serology Tests (HIV, HBsAg and antibody to HCV), Urine toxicology (cocaine (and metabolite), barbiturates, benzodiazepines, opiates, THC, methamphetamine/amphetamine, methadone and PCP), Urine pregnancy test, Serum $\beta$ -hCG test

Immunogenicity samples will be collected as described in [Table 3-2](#).

### 3.17 Vital Signs

Vital sign assessments including systolic and diastolic blood pressure (BP) [measured after sitting for at least 10 minutes], heart rate (HR), and oral temperature will be performed at each in-clinic study visit. Vital signs that are thought to be aberrant due to an error in measurement may be repeated. During screening and follow-up, a measurement that is a Grade 1 may be repeated once if the PI believes a transient condition led to the aberrant value.

Vital signs obtained at screening will serve as baseline values for the subject. Grade 1 values are allowable unless deemed clinically significant by the study investigator.

### 3.18 Electrocardiograms

A 12-lead ECG will be performed at screening and reviewed by the study PI or a co-Investigator to assess the cardiac status of a subject for eligibility for enrollment. ECGs will be performed after the subject rests quietly in a supine position for at least 10 minutes. To be eligible for participation, the QTc interval should be  $\leq 450$ ms, and there must be no clinically significant ECG abnormalities according to the study investigators and may be repeated once. ECG will be recorded at Screening visit.

### **3.19 Physical Examinations**

An abbreviated physical examination (PE) will be conducted at the screening visit and Day 0. Height and weight will be obtained at screening. An abbreviated PE is distinguished from a complete PE as all body system assessments are not required (e.g., pelvic, rectal, etc.).

On Day 0, the PE will focus assessment for the presence of the following in order to detect signs of a hypersensitivity reaction:

- General appearance including alertness and any difficulty breathing.
- HEENT (confirm no swelling of lips/tongue/uvula)
- Chest (confirm no stridor or wheezing)
- Heart (assess regularity of rhythm)
- Skin (confirm no hives, examine for any eruptions)
- Joints (confirm no swelling, warmth, or tenderness)

A symptom- directed PE will be performed at all other in-clinic study visits. Any new findings on examination post dosing or worsening of existing conditions are to be reported as AEs.

### **3.20 Other Safety Assessments**

#### **3.20.1 Hypersensitivity Panel**

A hypersensitivity panel includes cytokine and complement panels, IgE and tryptase. This 14 mL sample will be drawn on Day 0 prior to dosing. The sample will be processed only if the subject has a hypersensitivity reaction. If a subject develops anaphylaxis or anaphylactoid reaction, an additional 14 mL sample will be drawn during the event and another will be drawn after the event.

### **3.21 Protocol Deviation Reporting**

A protocol deviation is any noncompliance with the clinical trial protocol, GCP, or protocol-specific MOP requirements. The noncompliance may be either on the part of the subject, the investigator, or the study site staff. As a result of deviations, corrective actions are to be developed by the site and implemented promptly. All protocol deviations must be addressed in study subject source documents.

### **3.22 Medical and Surgical History**

Medical history will be obtained by direct interview. Subjects will be queried regarding a history of significant medical disorders of the head, eyes, ears, nose, throat (HEENT), mouth, cardiovascular system, lungs, gastrointestinal tract, liver, pancreas, kidney, urologic, nervous system, blood, lymph glands, endocrine system, musculoskeletal system, skin, and genital/reproductive tract. A history of any allergies, cancer, immunodeficiency, psychiatric

illness, substance abuse, and autoimmune disease will be solicited. The medical history will include current and past medical diagnoses, hospitalizations and major surgical procedures. The medical history will be obtained at screening and updated upon admittance to the unit on Day 0.

#### **4. CHANGES IN THE CONDUCT OF THE STUDY OR PLANNED ANALYSIS**

All analyses specified in this SAP are consistent with the final study protocol (Version 3.0, dated 7 Sept 2021).

Any changes in the analysis provided or any additional analysis performed will be documented in CSR.

---

## 5. QUALITY CONTROL AND QUALITY ASSURANCE METHODS FOR DATA ANALYSIS

Case report forms will be monitored and collected by ICON. All monitored CRFs will be sent to the Data Management group at ICON and processed according to the ICON Study Specific Procedure Data Management Plan (DMP). The DMP describes CRF data processing, edit checks, data query management, medical dictionary coding, SAE reconciliation, data transfers, and data quality review through database lock or any necessary reopening of the database. After database lock, the data will be retrieved from the database using SAS®.

## 6. PHARMACOKINETIC AND IMMUNOGENICITY ASSESSMENTS

### 6.1 Pharmacokinetic Assessment

Pharmacokinetic parameters for serum concentrations for each monoclonal antibody (NX01, NX02, NX11, XB10, XB18, and XB23) and serotypes (A and B) will be estimated separately using non-compartmental analysis (Phoenix™ WinNonlin®, version 8.0 or later; Certara L.P., Princeton, New Jersey, USA) and actual sample collection timepoints.

PK parameters will include, samples analysed using MNA method for Serotypes A and B:

Parameter	Definition
AUC (0-t)	Area under the concentration time-curve to the last concentration above the lower limit of quantitation
C max	Maximum observed concentration
T max	Time of maximum observed concentration

PK parameters will include, samples analysed using ECLA or ELISA method for each of the monoclonal antibodies of G03-52-01:

Parameter	Definition
AUC (0-∞)	Area under the concentration time-curve extrapolated to infinity
AUC (0-t)	Area under the concentration time-curve to the last concentration above the lower limit of quantitation
CL/F	Apparent oral clearance of drug following extravascular administration (total clearance)
C max	Maximum observed concentration
Kel	Elimination rate constant
t 1/2	Terminal elimination half-life
T max	Time of maximum observed concentration
V z/F	Volume of distribution during terminal phase following extravascular administration

AUC will be computed using the log-linear trapezoidal rule. The value of AUC%extrap should be less than or equal to 20% for the AUC(0-∞) to be considered well estimated. If this proportion is >20%, then the values of AUC(0-∞) will be treated with caution. When AUC(0-∞) is calculated and tabulated, the AUC%extrap will also be tabulated. Where AUC%extrap >20%, AUC(0-∞) and all related parameters (i.e. CL/F and Vz/F) will be presented but excluded from the calculation of summary statistics. All values excluded from the summaries should be flagged in the individual listings with an explanation for the exclusion.

The apparent terminal phase rate-constant (Kel) will be estimated by log-linear regression of the concentration-time data associated with this phase. The decision as to which data points describe

the terminal phase will be reached by inspecting the semi-logarithmic plot of the data, only considering concentrations at time points beyond  $T_{max}$ . A minimum of three data points will be used for the estimation of  $K_{el}$  preferably covering a time span of at least 2 times  $t_{1/2}$ . Ideally, the adjusted  $r^2$  value associated with the estimated  $K_{el}$  will be  $\geq 0.80$ . Poorly estimated  $K_{el}$  (i.e. if estimated over a time span less than 2 times  $t_{1/2}$  or adjusted  $R^2 < 0.80$ ), the corresponding  $t_{1/2}$  and other parameters derived using  $K_{el}$  (i.e.  $AUC_{(0-\infty)}$ ,  $CL/F$ ,  $V_z/F$ , and  $t_{1/2}$ ) will be flagged in the report and excluded from deriving PK parameters dependent on  $K_{el}$ .

In addition, population PK models will be developed for each of the monoclonal antibodies of G03-52-01 using nonlinear mixed-effect modelling. A separate Modelling & Simulation Analysis Plan will describe this analysis and the results will be reported separately to the CSR.

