#### 2.2.2 Secondary Endpoints

- The pharmacokinetic assessment of  $C_{max}$ ,  $T_{max}$  and  $AUC_{(0-t)}$  as measured by the validated Battelle Mouse Neutralization Assay (MNA) for serotypes A and B
  - Pharmacokinetic samples will be tested by MNA at pre-dose and on Days 4, 30, 60, 90, and 120 for Cohorts 1-3.
  - Pharmacokinetic samples will be tested by MNA at pre-dose, 2-hour post-dose (for future use), and on Days 4, 30, 45, 60, 90, and 120 for Cohort 4.
- The assessment of  $C_{max}$ ,  $T_{max}$ , half-life ( $\alpha$  and  $\beta$ ), MRT and  $AUC_{(0-t)}$  for each of the monoclonal antibodies of G03-52-01 as measured by a validated electrochemiluminescence assay (ECLA) or enzyme-linked immunosorbent assay (ELISA) method.

- PK samples will be tested by ECLA or ELISA at pre-dose, and at 2, 4, 8, 24, 48, and 72 hours post injection, and on Days 4, 8, 15, 30, 45, 60, 90, and 120 for Cohorts 1-3.
- Pharmacokinetic samples will be tested by ECLA or ELISA at pre-dose, 6 hours post dose, and on Days 1, 2, 4, 8, 15, 30, 45, 60, 90, 120, and 180 for Cohort 4.
- Samples will be tested to evaluate presence of anti-drug antibodies (ADA) collected for all cohorts.
  - Samples will be tested for ADA at pre-dose and on Days 15, 30, 45, 60, 90, and 120 for Cohorts 1-3.
  - Samples will be tested for ADA at pre-dose and on Days 45, 60, 90, 120, and 180 for Cohort 4.

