## 7.17 Pharmacokinetic Analysis

PK parameters will be summarized by dose levels using descriptive statistics for each monoclonal antibodies (NX01, NX02, NX11, XB10, XB18, and XB23) and serotypes (A and B), separately. PK Analysis Population will be used for all listings, concentration summary, PK parameter summary and graphical presentation.

The individual sampling and subject concentration-time will be listed and displayed graphically on linear and semi-log scales. The concentrations will be summarized descriptively by nominal time point in tabular and graphical formats (linear and semi-log scales) for each monoclonal antibodies (NX01, NX02, NX11, XB10, XB18, and XB23) and serotypes (A and B), separately. Summary statistics (n, mean, SD, coefficient of variation [CV%], median, minimum, maximum, geometric mean and geometric CV%) will be calculated for each time point. Geometric CV% will be calculated as the square root of the exponentiated SD of the natural log transformed data (SQRT(exp(sln2)-1), where appropriate.

Pharmacokinetic parameters for each monoclonal antibodies (NX01, NX02, NX11, XB10, XB18, and XB23) and serotypes (A and B) will be listed and summarized descriptively, including n, arithmetic mean, SD, minimum, median, maximum, CV(%), geometric mean, geometric CV%. For  $T_{max}$ , only n, minimum, median, and maximum will be reported.

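### Antibody AUC(0-t) can span 180 days in Cohort 4 but at most 120 days in Cohorts 1-3, so the by-dose summary may overstate exposure at 100 mg

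*SAP*

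**What the plan says.** SAP 2.2.2 names AUC(0-t) as the AUC endpoint for each antibody and for the neutralization assay. SAP 6.1 defines it in both parameter tables as "Area under the concentration time-curve to the last concentration above the lower limit of quantitation".

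The antibody (ECLA/ELISA) schedules in SAP 2.2.2 end on different days:
- Cohorts 1-3: early samples, then "on Days 4, 8, 15, 30, 45, 60, 90, and 120 for Cohorts 1-3".
- Cohort 4: pre-dose, 6 hours, then "on Days 1, 2, 4, 8, 15, 30, 45, 60, 90, 120, and 180 for Cohort 4".

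The neutralization assay (MNA) schedules end on the same day:
- Cohorts 1-3: "Pharmacokinetic samples will be tested by MNA at pre-dose and on Days 4, 30, 60, 90, and 120 for Cohorts 1-3".
- Cohort 4: pre-dose, an optional 2-hour sample, "and on Days 4, 30, 45, 60, 90, and 120 for Cohort 4".

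SAP 7.17 states that "PK parameters will be summarized by dose levels using descriptive statistics". SAP 6.1 also derives AUC(0-inf), CL/F, Vz/F and half-life for each antibody. AUC(0-inf), CL/F and Vz/F are left out of the summary statistics when more than 20% of AUC(0-inf) is extrapolated. SAP 6.1.2 treats concentrations below the limit of quantitation (LLOQ) as missing once a measurable value has been seen. Neither SAP 6.1 nor Protocol 10.3.4 lists an AUC over a common window or the time of the last quantifiable sample (t_last).

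**The concern.** For a long-lived antibody, the end of AUC(0-t) may be set by the visit schedule and not by the drug. The longer schedule applies only to the 100 mg cohort, so window length is completely confounded with the top dose. The secondary objective is PK across escalating doses. No dose-proportionality test is planned, so a reader will judge proportionality from the by-dose table. An extra 60 days of integration at 100 mg could look like a mild more-than-proportional rise that comes only from the schedule.

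**Working it through.** The documents give no half-life, LLOQ or AUC value, so there is no stated figure to reproduce. The check takes the same kinetics at every dose and asks what the schedule alone does.

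**Inputs from the documents.** Last antibody sample Day 120 or Day 180 (SAP 2.2.2); 20% extrapolation limit (SAP 6.1); 8 active subjects per cohort (SAP 3.1).

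**Assumptions.** One compartment, first-order absorption with half-life a = 2 days, terminal half-life h = 20 to 60 days, all samples quantifiable.

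**Formula.** The fraction of AUC(0-inf) remaining after day T is R(T) = [h·2^(−T/h) − a·2^(−T/a)] / (h − a). The ratio of interest is [1 − R(180)] / [1 − R(120)]. R(120) is also the percentage extrapolated in Cohorts 1-3, and R(180) that in Cohort 4.

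| h (days) | R(120) | R(180) | Ratio | Excess |
|---|---|---|---|---|
| 20 | 1.74% | 0.22% | 0.9978/0.9826 | 1.5% |
| 30 | 6.70% | 1.67% | 0.9833/0.9330 | 5.4% |
| 40 | 13.16% | 4.65% | 0.9535/0.8684 | 9.8% |
| 60 | 25.86% | 12.93% | 0.8707/0.7414 | 17.4% |

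**Check on the planned sampling times.** A linear-up/log-down trapezoid on each cohort's nominal times, with absorption half-lives of 1 and 2 days, gives Cohort 4 to Cohort 1-3 ratios of 1.013-1.015 (20 d), 1.051-1.053 (30 d), 1.095-1.098 (40 d) and 1.170-1.175 (60 d). Cutting Cohort 4 at Day 120 brings the ratio to 0.997-1.000 for half-lives of 10 to 90 days. The artefact goes, and Cohort 4's sparser early sampling costs at most 0.3%.

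**When AUC(0-inf) stops helping.** For simple terminal decline, 20% is extrapolated when 2^(−T/h) = 0.20, so h = T/2.322.
- Cohorts 1-3: 120/2.322 = 51.7 days (about 50.4 days with the 2-day absorption term).
- Cohort 4: 180/2.322 = 77.5 days.

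At 51.7 days the excess is (1 − 0.0894)/(1 − 0.20) − 1 = 13.8%. Between 51.7 and 77.5 days, the extrapolation rule would remove AUC(0-inf) from the Cohort 1-3 summaries and leave it in for Cohort 4. The SAP's Kel criteria apply as well.

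**When Day 180 is not quantifiable.** Take h = 20 days, absorption half-life 1.5 days and LLOQ at 1% of the 100 mg peak. The 100 mg profile then ends at Day 120, and the excess from Day 180 is zero. The 10 mg profile ends at Day 60, so dose-normalised AUC(0-t) at 100 mg exceeds that at 10 mg by 28.19/24.81 − 1 = 13.6%. This comes from the LLOQ alone and is the same with or without a Day 120 cut-off.

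**The case against.** The strongest reply is that the plan already has measures that do not depend on the window. AUC(0-inf), CL/F and half-life are derived for each antibody with the extrapolated percentage tabulated, and population PK models are planned. At half-lives of 20 to 40 days, extrapolation beyond Day 120 is 1.7% to 13.2%, inside the 20% limit, so AUC(0-inf) and CL/F can be compared across doses if Kel is acceptable. This stands for that range. It fails above about 52 days, where the excess is about 14% or more and AUC(0-t) may be the only AUC summarised at all four doses. The population models are reported outside the CSR.

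The second reply is that the effect is small for a descriptive analysis. With 8 subjects per dose and an assumed between-subject CV of 20% to 40%, the 95% interval for a ratio of two cohort geometric means is exp(±2.145 × √ln(1+CV²) × √(2/8)), a factor of about 1.24 to 1.51 either way. Dose escalation rests on safety data (Protocol 8.5.3 and 8.6.4), so no stated decision turns on AUC(0-t). That also stands, and it limits the importance of the point.

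A reader might infer three stronger things that the documents do not support:
- That 100 mg exposure is inflated as a matter of fact. This needs a quantifiable Day 180 sample and a long enough half-life, and neither is given.
- That the problem extends to MNA AUC(0-t). The definition is shared, but every cohort's MNA sampling ends at Day 120. Protocol Table 2 and the Day 180 visit list place no MNA sample there.
- That a Day 120 cut-off also repairs low-dose profiles lost early to the LLOQ. It does not; that is a separate mechanism.

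**Conclusion.** The point holds in a limited, conditional form. For the ECLA/ELISA antibody data, the by-dose AUC(0-t) summary may favour 100 mg because its window can be 60 days longer. The excess is about 1.5% at a 20-day half-life, 5.4% at 30, 9.8% at 40 and 17% at 60, and zero if Day 180 is below the LLOQ. These figures rest on assumed one-compartment kinetics that are the same at every dose. The gap in the plan matters most above a half-life of about 52 days, where AUC(0-inf) and CL/F drop out of the Cohort 1-3 summaries. This is a worthwhile refinement and does not threaten the study's conclusions.

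**What to change.** In SAP 6.1 and 7.17:
- Add a partial AUC(0-120 d) for each of the six antibodies in all four cohorts, and use it for the between-dose summary alongside AUC(0-inf).
- State how the value at 120 days is obtained. The SAP uses actual sampling times and the visit window is ±3 days, so interpolate where a later sample exists. Otherwise, including when the last quantifiable sample is earlier, extrapolate only with a Kel that meets the SAP's criteria. Flag such values.
- Report t_last by subject and dose level, so that unequal windows and early loss to the LLOQ are visible.
- Keep AUC(0-t) as the named secondary endpoint. No change is needed for the MNA.

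The cost is a partial-area setting and one or two table rows, with no new samples. Some low-dose values will rest on extrapolation or be flagged.

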### **3.10 Evaluation Pharmacokinetic and Sampling Schedule**

Six-mL samples of blood for PK samples will be drawn at the following times: pre-dose, and at 2, 4, 8, 24, 48, and 72 hours post dose and on Days 4, 8, 15, 30, 45, 60, 90, and 120 for cohorts 1-3 & pre-dose, at 6 hours post-dose, and on days 1, 2, 4, 8, 15, 30, 45, 60, 90, 120 and 180 for cohort 4. Serum will be analyzed for levels of each of the monoclonal antibodies using a validated ECLA or ELISA. All PK samples will be tested by ECLA or ELISA.

Three 10-mL samples of blood will be drawn to be analyzed for neutralizing antibody concentrated using the validated Battelle MNA. PK samples will be tested by the Battelle MNA for serotypes A and B at pre-dose and on Days 4, 30, 60, 90, and 120 for cohorts 1-3 & at pre-dose, and on days 4, 30, 45, 60, 90 and 120 for cohort 4.

PK samples will be collected as described in [Table 3-2](#).

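### The two-half-life span rule for Kel removes long half-lives, and its ceiling is 30 days lower in Cohorts 1-3 than in Cohort 4, so follow-up length alone can produce an apparent rise at 100 mg

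*SAP*

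**What the plan says.** SAP 6.1 estimates Kel by log-linear regression on points chosen by eye from the semi-logarithmic plot, restricted to samples later than Tmax. At least three points are required, and the length of the regression is first worded as a preference: "preferably covering a time span of at least 2 times" the half-life. That preference then becomes a criterion. Kel is poorly estimated "i.e. if estimated over a time span less than 2 times" the half-life, or if adjusted R² is below 0.80. In that case the half-life and the other Kel-based parameters "will be flagged in the report and excluded from deriving PK parameters dependent on" Kel. The parameters named are AUC(0-∞), CL/F, Vz/F and t½.

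The same section has a second rule. When more than 20% of AUC is extrapolated, AUC(0-∞), CL/F and Vz/F "will be presented but excluded from the calculation of summary statistics". Half-life is not on that list.

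One set of rules covers all cohorts, but the sampling does not. SAP 2.2.2 samples Cohorts 1-3 at early "hours post injection, and on Days 4, 8, 15, 30, 45, 60, 90, and 120 for Cohorts 1-3". SAP 3.10 samples "pre-dose, at 6 hours post-dose, and on days 1, 2, 4, 8, 15, 30, 45, 60, 90, 120 and 180 for cohort 4". SAP 7.17 summarises the parameters descriptively by dose level. Population PK models are planned for each antibody, but SAP 6.1 has them reported separately from the clinical study report.

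**The concern.** The test for keeping a half-life uses the half-life itself. A subject with slow elimination fails because elimination is slow, even if the fit is good. This truncates the distribution from above, and the cut-off depends on how long the subject was followed.

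Follow-up length is fully confounded with dose: only the 100 mg cohort is sampled to Day 180. If all four doses share one true half-life, the retained values still average lower at 10, 25 and 50 mg than at 100 mg. A reader of the by-dose table could take this for dose-dependent elimination. To the extent that slow elimination reflects low clearance, CL/F would shift the other way.

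Half-life of each antibody is a secondary endpoint, and each cohort has 8 active subjects, so losing one or two values can move a summary. The bias also has the same sign for all six antibodies and for each of Cohorts 1-3, so it would not average out across tables.

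**Working it through.** The plan states no expected half-life and no ceiling, so there is no figure of its own to reproduce.

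**Inputs from the documents.** Span rule of 2 × t½ (SAP 6.1). Last PK day 120 or 180 (SAP 2.2.2 and 3.10). 8 active subjects per cohort (SAP 3.1).

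**Assumptions.** True half-life 20 to 40 days, between-subject CV 30% or 35%, terminal phase starting at Day 15, 30 or 45, and all samples quantifiable to the last visit.

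**Step 1: ceiling.** Keeping t½ requires (last day − start) ≥ 2 × t½, so the largest retainable value is (last day − start)/2.

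| Start | Cohorts 1-3 | Cohort 4 |
|---|---|---|
| Day 15 | (120−15)/2 = 52.5 d | (180−15)/2 = 82.5 d |
| Day 30 | (120−30)/2 = 45 d | (180−30)/2 = 75 d |
| Day 45 | (120−45)/2 = 37.5 d | (180−45)/2 = 67.5 d |

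The gap is (180−120)/2 = 30 days at any common start. The ceiling falls further if a low-dose profile drops below the quantitation limit early. From a Day 15 start it is (90−15)/2 = 37.5 days if Day 90 is the last usable sample, and (60−15)/2 = 22.5 days if Day 60 is.

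**Step 2: effect on the summary.** Take log-normal half-lives with geometric mean g and log-scale SD s = √ln(1+CV²), which is 0.294 at CV 30% and 0.340 at CV 35%. With ceiling c and z = ln(c/g)/s, the share excluded is 1−Φ(z) and the retained geometric mean is g·exp(−s·φ(z)/Φ(z)). Each pair below is Cohorts 1-3 against Cohort 4.

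| CV, start | True t½ | Excluded | Retained geometric mean | False rise |
|---|---|---|---|---|
| 30%, Day 15 | 20 d | 0.1% vs 0% | 20.0 vs 20.0 | 0.1% |
| | 25 d | 0.6% vs 0% | 24.9 vs 25.0 | 0.5% |
| | 30 d | 2.8% vs 0% | 29.4 vs 30.0 | 1.9% |
| | 40 d | 18% vs 0.7% | 36.5 vs 39.8 | 9% |
| 30%, Day 30 | 20 d | 0.3% vs 0% | 19.9 vs 20.0 | 0.3% |
| | 25 d | 2.3% vs 0% | 24.6 vs 25.0 | 1.6% |
| | 30 d | 8.4% vs 0.1% | 28.6 vs 30.0 | 5% |
| | 40 d | 34% vs 1.6% | 33.9 vs 39.5 | 17% |
| 35%, Day 45 | 20 d | 3.2% vs 0% | 19.5 vs 20.0 | 2.5% |
| | 25 d | 12% vs 0.2% | 23.2 vs 25.0 | 8% |
| | 30 d | 26% vs 0.9% | 25.9 vs 29.8 | 15% |
| | 40 d | 58% vs 6% | 29.2 vs 38.3 | 31% |

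**Step 3: check on fitted profiles.** 40,000 mono-exponential profiles were simulated at the nominal days with 15% residual CV. Kel was fitted and both the span and the R² rules were applied. For a true 40 days, start Day 30 and CV 30%, exclusions were 35% vs 2% and retained geometric means 33.5 vs 39.4 days, close to Step 2. In these runs (starts at Day 15 and Day 30) the R² rule added at most 0.4 percentage points to the exclusions.

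**Step 4: chance of losing a subject.** At 30 days, start Day 30 and CV 30%, the chance that at least one of 8 is excluded is 1−(1−0.084)⁸ ≈ 50% in each of Cohorts 1-3, and 1−(1−0.0009)⁸ ≈ 1% in Cohort 4.

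**Step 5: the 20% extrapolation rule.** Under mono-exponential decline the extrapolated share is exp(−ln2·T/t½). Holding it at or below 0.20 needs t½ ≤ T·ln2/ln5, which gives 51.7 days (T = 120) against 77.5 days (T = 180). This is approximate for an intramuscular dose.

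**The case against.** - **The size may be negligible.** This stands as a limit. The SAP fixes no start for the terminal phase, and usable samples exist from Day 8. At 20-25 days with a start at Day 15 or 30, almost nothing is lost. The 31% figure needs a 40-day half-life, a Day 45 start and CV 35% together.
- **The SAP does not plainly say that half-lives leave the summaries.** This also stands. The Kel sentence speaks of exclusion from derivation, while the extrapolation rule names summary statistics outright. Because t½ is itself on the list of Kel-dependent parameters, removal is the natural reading, but the ambiguity is a defect in its own right.
- **No between-dose test is planned, and 8 subjects per cohort give wide uncertainty.** True: at CV 30% the standard error of a log-ratio of two cohorts is 0.294 × √(2/8) ≈ 0.15, larger than the shifts up to 30 days. Systematic bias of one sign across six antibodies is still worth avoiding when it costs so little.
- **Limits on span and fit are a legitimate reliability choice, and population PK is planned.** Agreed, so the rule need not be abandoned. Listings flag values left out of summaries, but no count per dose and no with-and-without summary is specified for this rule.

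Three stronger readings are tempting and the documents do not support them. The rule does not truncate the lower doses only, since Cohort 4 has a ceiling too. The extrapolation rule does not bias half-life, because it acts on AUC(0-∞), CL/F and Vz/F. The longer half-life claimed in protocol 2.2 is not threatened: it is an advantage over equine antitoxins, whose current product has a half-life of 8-34 hours (protocol 2.1.2), and a downward bias is conservative for that claim.

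**Conclusion.** The point holds in a conditional form. Retention of t½ and its derived parameters depends on the half-life itself, with a ceiling 30 days lower in Cohorts 1-3 at any common start if both groups are quantifiable to their last sample. That much follows from the text alone.

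The size of the resulting false rise at 100 mg rests on assumed half-life, variability and start of the terminal phase. It is negligible to small at 20-25 days with an early start, modest at 30 days, and material from about 40 days. It becomes material sooner with a late start, or if low-dose profiles become unquantifiable before Day 120. Comparisons among 10, 25 and 50 mg share one nominal window and are affected only if quantifiability differs. Cmax, Tmax and AUC(0-t) are not touched by either rule. The change is worth making because it is cheap, not because a large bias has been shown.

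**What to change.** In SAP 6.1 and 7.17:

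1. State whether flagged t½ values leave the summary statistics, and make the sentence that prefers a two-half-life span agree with the sentence that excludes.
2. Keep the reliability rule for the main summary. Add a second summary of t½, AUC(0-∞), CL/F and Vz/F that includes the flagged values.
3. Report the number excluded per dose and antibody, by reason (span, R², extrapolation).
4. For any comparison of these parameters across doses, re-estimate Cohort 4 Kel on samples to Day 120, or cite the population PK estimate already planned. From Day 4 to Day 120 the nominal sampling days are the same in all cohorts, so this gives a like-for-like window.

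No visit, sample or assay changes. The cost is SAP wording and one extra PK table. The downside is that the second summary contains some less precise, flagged half-lives, which is why it should not replace the main one.
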